12.2 Primary Objective: 30-day procedure and/or device related stroke rate

12.2.1 Objective

Demonstrate that the observed incidence of procedure and/or device related incidence of new stroke (excludes transient ischemic attack) within 30 days of an ablation procedure (index or reablation) with the Phased RF System is less than 1.8% with observed upper confidence boundary that is less than 3.5%.

12.2.2 Hypothesis

To pass the primary objective the following two conditions must be met:

1. The observed procedure and/or device related stroke rate must be less than 1.8%.
2. The exact one-sided upper 95% confidence interval for the procedure and/or device related stroke rate must be less than 3.5%.

The formal statistical hypothesis for the primary objective is:

$H_0: \pi \geq 3.5\%$

$H_a: \pi < 3.5\%$

where π is the true 30-day post ablation procedure (index or reablation) procedure and/or device related stroke rate.

12.2.3 Definition of procedure and/or device related stroke

Procedure and/or device related strokes are defined as events classified by the CEC meeting all of the requirements in Table 5. Specifically, the stroke must have a symptom onset date within 30 days of an ablation procedure where at least one phased RF catheter is deployed into the left atrium and be considered related to the procedure and/or device by the CEC.

12.2.4 Rationale for stroke threshold

The peri-procedural stroke rate is not well characterized in the persistent and long-standing persistent AF population. The observed procedure or device related stroke rate among the 176 ablated subjects in the TTOP-AF study was

2.8% with an upper one-sided 95% confidence interval of 5.9%. However, the FDA Center for Devices and Radiological Health's cardiac devices advisory panel indicated that both the observed stroke rate and its associated upper confidence boundary in the TTOP-AF study were too high to enable approval of the phased RF ablation system. Medtronic has identified several mitigation strategies that are expected to lower the peri-procedural stroke rate. With these mitigation strategies enforced in the current protocol, Medtronic believes the true procedure and/or device related peri-procedural stroke rate will be less than 1.8%, a value similar to the peri-procedural stroke rates reported in recent observational studies.

Specifically, a single site registry study by Patel et al., reported a 1.8% per-procedural stroke rate (one-sided upper 95% CI: 2.6%) among 1209 subjects with persistent or long-standing persistent AF undergoing off label AF ablation. Additionally, Patel et al. found that persistent AF was the only independent predictor of peri-procedural stroke risk in a multivariable analysis. A similar study was performed by Spragg et al, evaluating 517 subjects with atrial fibrillation. The stroke rate was 1.7% (95% one-sided UCB; 3.8%) for the 240 subjects with persistent atrial fibrillation. A key limitation with these observational trials is that the studies' did not require rigorous follow-up protocols and therefore the stroke rates may be under reported.

After considering all available data sources together with close consultation with the FDA, a procedure and/or device related peri-procedural stroke threshold of 3.5% was chosen. This threshold is greater than the upper one-sided 95% confidence intervals reported by Spragg et al and Patel et al but is lower than the upper confidence interval for the peri-procedural stroke rate observed in the TTOP-AF study. Additionally, a peri-procedural stroke threshold of 3.5% mandates that the observed study stroke rate must be less than 1.8% for study success for a sample size of at least 300 ablated subjects.

12.2.5 Experimental design and analysis methods

This study is a prospective, unblinded, multi-center, worldwide clinical study designed to evaluate the procedure and/or device related peri-procedural stroke rate within 30 days of an ablation procedure with the Phased RF System. The study will be considered successful if the primary objective is met. A single decision regarding study success will be made once all subjects with a Phased RF ablation procedure have had the opportunity for a reablation procedure (completed the 6-month visit) or completed the 30-day post-reablation visit if a reablation is required. Alternatively, the study may stop early for futility if more than six (6) procedure and/or device related peri-procedural strokes occur prior to completing enrollment.

For computing the peri-procedural stroke rate, the denominator will be all subjects with at least one ablation procedure attempt where at least one of the Phased RF catheters was deployed into the left atrium and have at least 30 days of post-

procedure follow-up. Also, subjects who have a procedure and/or device related peri-procedural stroke as classified by the CEC with symptom onset date within 30 days of a Phased RF ablation procedure will be included. The numerator for the stroke rate will be all subjects included in the denominator that had a procedure and/or device related stroke as classified by the CEC with a symptom onset date within 30 days of a Phased RF ablation procedure. The null hypothesis will be rejected in favor of the alternative if the observed stroke rate is less than 1.8% and the exact one-sided upper 95% confidence interval is less than 3.5%.

Additionally, a one-sided exact p-value will be computed for comparing the observed stroke rate to the performance goal of 3.5%.

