1.11 Sample Size

Up to 420 subjects will be enrolled to ensure that at least 300 subjects receive an index Phased RF ablation procedure and can be evaluated for the primary safety endpoint. Subject enrollment will stop once approximately 300 evaluable subjects are accrued.

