10. ADVERSE EVENTS AND DEVICE DEFICIENCIES

Timely, accurate, and complete reporting and analysis of safety information for clinical studies is crucial for the protection of subjects, investigators, and the sponsor. Reporting and analysis of safety data is mandated by regulatory authorities worldwide. Medtronic (sponsor) has established Standard Operating Procedures (SOPs) in conformity with worldwide regulatory requirements to ensure appropriate reporting of safety information. This study is conducted in accordance with these SOPs and regulations.

Since the safety reporting requirements and classification systems vary for each regulatory agency and per applicable regulation, requirements from all geographies are taken into account for the collection and reporting of safety information.

There are no adverse event (AE) stopping rules tied to the collection and reporting of AEs for this study, except for those rules identified in the regulatory requirements. However, if more than six (6) strokes that meet the definition of the primary safety endpoint as described in Table 5 occur prior to completing enrollment, the study may stop early for futility.

For any changes in status of a previously reported AE (i.e. change in action, change in outcome, change in relatedness, change in seriousness), an AE update must be completed.

All AEs must be followed until resolved, ongoing without further actions to be taken, the subject exits the study or until study closure, whichever occurs first. In the event that a subject is exited from the study prior to study closure, all efforts should be made to continue following the subject until all ongoing AEs are resolved or they are ongoing without further actions to be taken.

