10.5 Data Monitoring Committee (DMC)

Ongoing oversight for this study will be provided by an independent DMC. The DMC will consist of a minimum of at least one electrophysiologist, one neurologist, and one statistician who are not sponsor employees. The DMC will not include participating VICTORY AF investigators, members of the Steering Committee or Clinical Events Committee.

The DMC is retained to aid the sponsor in safeguarding the interests of trial participants and monitoring the overall conduct of the study. The DMC will meet at regular intervals or as

agreed upon to review accumulating study data and will be advisory to the sponsor and may provide recommendations for early termination of the trial. Review and consensus by the entire committee is required to recommend that the study should be stopped. The DMC may also make recommendations related to the selection, management and retention of subjects, improvement of adherence to protocol-specified regimens, and procedures for data management and quality control.

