12.2.6 Sample size and power

[figure not shown]
A sample size of 300 subjects completing the 30-day post procedure follow-up visit and having the opportunity for a reablation procedure (i.e. completing the 6-month follow-up visit) or having a reablation procedure and completing the 30-day post-reablation visit provides at least 80% power to test the primary study hypothesis given the following assumptions:

1. One-sided type I error rate of 0.05
2. Exact test of a binomial proportion versus a fixed performance goal of 3.5%
3. Observed stroke rate must be less than 1.8%.
4. Assumed true stroke rate is 1.3%

Figure 1 displays the power of the study to meet its primary objective when the true stroke rate ranges from 0.1% to 3.5% and 300 subjects complete the 30-day post-ablation (or reablation) visit and have had the opportunity for a reablation procedure. Specifically, the study has 90% power if the true stroke rate is 1%, 80% power if the true stroke rate is 1.3%, and 55% power if the true stroke rate is 1.8%. Figure 1 also demonstrates that the type I error is less than 5% when the true stroke rate is 3.5%.

Assuming an annualized attrition rate of 10% following the index ablation procedure, a uniform reablation rate of 30% within 180 days of the index ablation procedure, and a conservative 26% pre-procedure attrition rate up to 420 enrolled subjects will be required to ensure that at least 300 subjects complete the 30-day post ablation follow-up visit and have the opportunity for a reablation procedure or have a reablation procedure and complete the 30-day post-reablation procedure visit. Note that it is not anticipated that all 420 subject enrollments will be required, since study enrollment will cease once enough subjects have completed an index Phased RF procedure to ensure that the target sample size of 300 evaluable subjects can be obtained.

Figure 1: Study Power versus True Stroke Rate

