### 2.2 Study Scope

The study is expected to be conducted at approximately 40 centers located in Europe, Canada and the United States. A maximum of 350 subjects will be enrolled in the study to ensure 300 subjects can be evaluated for the primary safety endpoint. Subjects will be followed for 30 days post reablation (if reablation required) procedure or 6 months post index procedure (if no reablation procedure required) for the primary safety objective. The primary safety objective will be evaluated after at least 300 ablated subjects complete the 30 day post index or reablation procedure visit and have had the opportunity for a reablation. Alternatively, the study may stop early for futility prior to completing enrollment if more than 6 procedure and/or device related strokes occur within the 30 day peri-procedural period.

Study subjects from all geographies will be followed for 6 months following their final ablation procedure, or official study closure defined as when Medtronic and/or regulatory requirements have been satisfied per the Clinical Investigational Plan (CIP), whichever occurs first. Accordingly, the expected total study duration is approximately 36 months, representing 24 months of enrollment and up to 12 months of subject follow-up.

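### At the planned analysis size the futility limit of more than six strokes is set one stroke past the point where the success rule is already lost

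*Protocol*

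**What the plan says.** The success rule has two parts (Protocol 12.2.2, SAP 3.2.1): the observed rate must be below 1.8%, and the exact one-sided 95% upper confidence bound must be below 3.5%.

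The futility rule in Protocol 12.2.5 is that "the study may stop early for futility if more than six (6) procedure and/or device related peri-procedural strokes occur prior to completing enrollment". Protocol 1.3, 2.2 and 6.1 and SAP 2.2, 3.1.4.1 and 3.2.3 carry the same limit. Protocol 10 repeats it as the only numeric stroke limit in the plan: "if more than six (6) strokes that meet the definition of the primary safety endpoint". Neither document derives the number six.

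The planned size is 300 evaluable subjects. Protocol 1.11 states: "Subject enrollment will stop once approximately 300 evaluable subjects are accrued". Protocol 12.2.4 ties the rate condition to that size: "the observed study stroke rate must be less than 1.8% for study success for a sample size of at least 300 ablated subjects". Protocol 12.2.6 reports that "the study has 90% power if the true stroke rate is 1%, 80% power if the true stroke rate is 1.3" per cent, adds 55% power at 1.8%, and says that "the type I error is less than 5% when the true stroke rate is 3.5" per cent. SAP 3.2.4 gives the same figures.

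The enrolment caps differ. The protocol allows 420 with 26% pre-procedure attrition. The SAP states: "A maximum of 350 subjects will be enrolled in the study to ensure 300 subjects can be evaluated for the primary safety endpoint", with 11% attrition.

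**The concern.** A reader takes a futility limit expressed as a stroke count to be the point at which the trial can no longer succeed. Here the limit is reached at the seventh stroke, while the success rule at the planned size is lost at the sixth. The power section treats a sixth stroke as failure, and the section just before it does not treat that stroke as futile.

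The trial exists because an advisory panel judged stroke risk too high in the earlier study, where the rate was 2.8% (Protocol 3 and 12.2.4). After a sixth stroke the written number gives the DMC and the sponsor no reason to stop, and subjects can still be ablated in a trial that fails at its planned denominator.

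**Working it through.** **Inputs.** Rate limit 1.8% and bound limit 3.5% (Protocol 12.2.2); one-sided alpha 0.05, n = 300, and the stated power and type I error (Protocol 12.2.6); caps and attrition of 420 and 26% (Protocol 12.2.6) and 350 and 11% (SAP 3.2.4).

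**1. Reproduce the stated power.** Power = P(X ≤ k), with X binomial(300, p) and k the largest passing count.

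| k | p = 1% | p = 1.3% | p = 1.8% | p = 3.5% (type I error) |
|---|---|---|---|---|
| Plan states | 90% | 80% | 55% | < 5% |
| 4 | 81.6% | 64.9% | 37.1% | 1.95% |
| 5 | 91.7% | 80.2% | 54.6% | 4.76% |
| 6 | 96.7% | 90.1% | 70.3% | 9.76% |

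Only k = 5 fits. The stated figures are correct, and they count a sixth stroke as failure.

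**2. Largest passing count by denominator.** The exact (Clopper-Pearson) upper bound is the 0.95 quantile of Beta(x + 1, n − x).

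| Strokes / n | Rate | Upper bound | Result |
|---|---|---|---|
| 5/298 | 1.68% | 3.495% | pass |
| 5/300 | 1.67% | 3.472% | pass |
| 6/300 | 2.00% | 3.909% | fails both |
| 5/311 | 1.61% | 3.351% | pass |
| 6/311 | 1.93% | 3.772% | fails both |
| 6/335 | 1.791% | 3.504% | fails on the bound |
| 6/336 | 1.786% | 3.494% | pass |
| 6/350 | 1.71% | 3.355% | pass |

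The maximum is 4 for n = 259 to 297, 5 for n = 298 to 335, and 6 for n = 336 to 388. At 388, seven strokes give 1.804% and fail the rate condition.

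**3. Which denominator the plan implies.** Protocol: 420 × 0.74 = 310.8. SAP: 350 × 0.89 = 311.5. Both give about 311 ablations, where the maximum is 5. Reaching 336 would need pre-procedure attrition of at most 1 − 336/420 = 20% under the protocol cap, or 1 − 336/350 = 4% under the SAP cap.

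**4. Exposure after the sixth stroke.** Assume 311 ablations, one chance of stroke per subject at rate p, and strokes known at once. The sixth stroke falls on subject t with probability Binom(5; t − 1, p) × p. The expected number of further ablations until the seventh stroke or the end is (1 − (1 − p)^(311 − t))/p. Sum over t = 6 to 310.

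| True rate | Sixth stroke before last subject | Further ablations in those trials | Averaged over all trials |
|---|---|---|---|
| 1.3% | 21.9% | 40 | 8.8 |
| 1.8% | 48.6% | 38 | 18.3 |
| 2.8% | 86.7% | 32 | 27.5 |
| 3.5% | 96.2% | 27 | 26.3 |

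**5. Reporting delay.** With even accrual over 24 months (730 days, an assumption), a 30-day delay covers about 311 × 30/730 = 12.8 ablations, and a 60-day delay about 25.6. By simulation, the share of trials in which the sixth stroke is known before the last ablation becomes:

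| True rate | 30-day delay | 60-day delay |
|---|---|---|
| 1.3% | 19.5% | 16.7% |
| 1.8% | 44.8% | 40.7% |
| 2.8% | 84.2% | 81.0% |
| 3.5% | 95.1% | 93.4% |

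**The case against.** **The denominator is not fixed.** The plan says at least 300, and every ablated subject with 30 days of follow-up is analysed. The 26% attrition is described as conservative, and the SAP's 11% under the protocol's cap would give 420 × 0.89 = 373.8 ablations. Subjects who have consented but are not yet ablated when enrolment closes could also push the total past 336. Across 336 to 374, six strokes pass and seven fail (7/374 = 1.87%), so the limit would then be exact. This is arithmetically right, but it combines one document's cap with the other's attrition, or assumes a backlog that neither document describes. Each document's own figures give about 311, and enrolment is meant to stop at approximately 300 evaluable. Neither document offers a larger size as the reason for the limit.

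**The rule is permissive.** It says the study may stop. The DMC "may provide recommendations for early termination of the trial" without reference to any count, and the sponsor can suspend the study on safety grounds (Protocol 7.16.3). This stands: nothing obliges the trial to continue after six strokes. It does not justify a number that disagrees with the success rule.

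**The exposure figures are idealised.** This stands too. Strokes after reablation, and the time taken for adjudication, would come later than even the 60-day delay. The largest percentages belong to true rates well above the design rate of 1.3%.

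**Strokes versus subjects.** The futility rule counts strokes, while the success numerator counts subjects. Six strokes in five subjects would still pass at 300. This is correct but rare, and it does not rescue the limit.

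**Conclusion.** The concern holds. For any analysed denominator from 298 to 335, a sixth subject with a qualifying stroke ends the chance of success, and the futility limit is not reached until the seventh stroke. The stated power and type I error are right and rest on a maximum of five; the futility number is what is out of line. Because the limit lies beyond the failure point and is not binding, it neither lowers power nor raises type I error at that size.

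The cost is possible exposure: on average 8.8 further ablations per trial at a true rate of 1.3% and 18.3 at 1.8%, with 311 ablations, immediate knowledge of strokes and no discretionary stop. The conclusion depends on the denominator staying at 335 or below, as the plan's own figures imply. It should be fixed, but it does not threaten the primary analysis.

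**What to change.** Define the futility limit as the largest passing count at the planned analysis size plus one. For a denominator of 300 to 335 that is six or more. State that denominator, say that it will not be extended in response to the stroke count, and count subjects with a qualifying stroke so that the limit matches the success numerator. Make the same change in Protocol 1.3, 2.2, 6.1, 10 and 12.2.5 and in SAP 2.2, 3.1.4.1 and 3.2.3.

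If 336 to 388 analysed subjects are intended, state that size, keep more than six, and restate the power for it.

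The cost is a wording amendment to both documents and no extra subjects. No power is lost at 335 or fewer, because six fails there in any case. The risk is a denominator that unexpectedly reaches 336: at exactly that size and a true rate of 1.3%, stopping at six would cut power from P(X ≤ 6) = 84.9% to P(X ≤ 5) = 72.6%, a loss of 12.3 points. That is why the limit must be tied to a stated size.

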12.2.6 Sample size and power

[figure not shown]
A sample size of 300 subjects completing the 30-day post procedure follow-up visit and having the opportunity for a reablation procedure (i.e. completing the 6-month follow-up visit) or having a reablation procedure and completing the 30-day post-reablation visit provides at least 80% power to test the primary study hypothesis given the following assumptions:

1. One-sided type I error rate of 0.05
2. Exact test of a binomial proportion versus a fixed performance goal of 3.5%
3. Observed stroke rate must be less than 1.8%.
4. Assumed true stroke rate is 1.3%

Figure 1 displays the power of the study to meet its primary objective when the true stroke rate ranges from 0.1% to 3.5% and 300 subjects complete the 30-day post-ablation (or reablation) visit and have had the opportunity for a reablation procedure. Specifically, the study has 90% power if the true stroke rate is 1%, 80% power if the true stroke rate is 1.3%, and 55% power if the true stroke rate is 1.8%. Figure 1 also demonstrates that the type I error is less than 5% when the true stroke rate is 3.5%.

Assuming an annualized attrition rate of 10% following the index ablation procedure, a uniform reablation rate of 30% within 180 days of the index ablation procedure, and a conservative 26% pre-procedure attrition rate up to 420 enrolled subjects will be required to ensure that at least 300 subjects complete the 30-day post ablation follow-up visit and have the opportunity for a reablation procedure or have a reablation procedure and complete the 30-day post-reablation procedure visit. Note that it is not anticipated that all 420 subject enrollments will be required, since study enrollment will cease once enough subjects have completed an index Phased RF procedure to ensure that the target sample size of 300 evaluable subjects can be obtained.

Figure 1: Study Power versus True Stroke Rate

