2.2 Study description

The study is expected to be conducted at up to 55 centers located in Europe, Canada and the United States to support US Food and Drug Administration (FDA) marketing application. A maximum of 420 subjects will be enrolled in the study to ensure 300 subjects can be evaluated for the primary safety endpoint. Subjects will be followed for 30 days post reablation (if reablation required) procedure or 6 months post index procedure (if no reablation procedure required) for the primary safety objective. The primary safety objective will be evaluated after at least 300 ablated subjects complete the 30 day post index or reablation procedure visit and have had the opportunity for a reablation visit. Alternatively, the study may stop early for futility if more than 6 procedure and/or device related strokes occur within the 30 day peri-procedural period prior to completing enrollment.

Study subjects from all geographies will be followed for 6 months following their final ablation procedure, or official study closure defined as when Medtronic and/or regulatory requirements have been satisfied per the Clinical Investigational Plan (CIP), whichever occurs first. Accordingly, the expected total study duration is approximately 36 months, representing 24 months of enrollment and up to 12 months of subject follow-up.

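### The stated power of at least 80% is right at 300 analysed subjects, but the primary denominator implied by the plan is about 308 to 312, where power is about 78 to 79%

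*Protocol*

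**What the plan says.** Protocol 12.2.6 and SAP 3.2.4 make the same power statement. A sample of 300 "provides at least 80% power to test the primary study hypothesis given the following assumptions": "One-sided type I error rate of 0.05", an exact binomial test against 3.5%, an observed rate below 1.8%, and a true rate of 1.3%. Both sections also give 90% power at a true rate of 1.0% and 55% at 1.8%. The 300 are subjects who complete the 30-day visit and have had the opportunity for a reablation (by completing the 6-month visit), or who are reablated and complete the 30-day visit after that.

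Protocol 12.2.5 and 12.2.7 define the primary denominator more widely: all ablated subjects with at least 30 days of follow-up, plus anyone with an endpoint stroke. Under 12.2.8, a subject who leaves after the 30-day visit but before the 6-month visit or a reablation stays in, counted as having no stroke. Under 12.2.5 the single decision waits for all ablated subjects, so the protocol does not cap the analysis at 300.

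The documents describe the target of 300 in different ways:
- Protocol 2.2: "The primary safety objective will be evaluated after at least 300 ablated subjects complete the 30 day post index or reablation procedure visit".
- Protocol 1.11: at least 300 who receive an index procedure and can be evaluated, followed by "Subject enrollment will stop once approximately 300 evaluable subjects are accrued".
- SAP 3.1.4.1: the cutoff is the day 300 ablated subjects have finished the window, and a subject who exited before any reablation counts toward them.

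**The concern.** Success requires an observed rate below 1.8% and also "The exact one-sided upper 95% confidence interval for the procedure and/or device related stroke rate must be less than 3.5" (per cent). Together these set a whole number of permitted strokes at each sample size. Between the sizes at which that number rises, each added subject adds expected strokes without adding a permitted one, so power falls. The plan computes power at one size, while its denominator rule leads to a larger one. The primary test is the sole criterion for study success and turns on a single stroke, yet neither document's text gives the permitted count, or power for any size other than 300.

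**Working it through.** **Inputs.** One-sided alpha 0.05, goal 3.5%, observed-rate limit 1.8%, true rate 1.3%, 10% annual attrition, 30% reablation uniform over 180 days, 26% pre-procedure loss and at most 420 enrolled (Protocol 12.2.2 and 12.2.6). Denominator rule from Protocol 12.2.5, 12.2.7 and 12.2.8. Assumption not in the documents: exits follow a constant hazard.

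**Formulas.** The limit c(n) is the largest x with x/n < 1.8% and U(x, n) < 3.5%, where U is the exact (Clopper-Pearson) one-sided 95% upper bound, i.e. the 95th percentile of Beta(x+1, n−x). Power is P(X ≤ c) for X ~ Binomial(n, p).

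**Step 1: reproduce the plan at n = 300.** 5/300 = 1.67% and U(5, 300) = 3.472%, so 5 strokes pass. U(6, 300) = 3.909%, so 6 fail and c = 5. At p = 1.3% the probabilities of 0 to 5 strokes sum to 0.0197 + 0.0780 + 0.1535 + 0.2009 + 0.1964 + 0.1532 = 0.8017. Power is 91.7% at 1.0% and 54.6% at 1.8%, and type I error is 4.76%. These agree with the stated figures.

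**Step 2: the size the plan's rules imply.** Retention to day d is S(d) = 0.9^(d/365), so S(30) = 0.9914 and S(180) = 0.9494. For a reablation at day u, uniform on 0 to 180, the mean of S(u + 30) is 0.9661.
- Share completing the window: 0.7 × 0.9494 + 0.3 × 0.9661 = 0.9544.
- For 300 completers: 300 / 0.9544 = 314.3 ablated, and 314.3 × 0.9914 = 311.6, about **312 analysed**.
- At the enrolment ceiling: 420 × 0.74 = 310.8 ablated, and 310.8 × 0.9914 = 308.1, about **308 analysed**. (310.8 × 0.9544 gives about 297 window completers, but that is not the primary denominator.)
- The SAP's 350 enrolled with 11% pre-procedure loss gives 311.5 ablated and about 309 analysed.

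**Step 3: exact power.**

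| Analysed n | Permitted strokes | Power at 1.3% | Power at 1.8% | Type I error |
|---|---|---|---|---|
| 297 | 4 | 65.6% | 38.0% | 2.10% |
| 298 | 5 | 80.6% | 55.2% | 4.96% |
| 300 | 5 | 80.2% | 54.6% | 4.76% |
| 301 | 5 | 79.97% | 54.2% | 4.66% |
| 304 | 5 | 79.4% | 53.3% | 4.37% |
| 308 | 5 | 78.6% | 52.1% | 4.02% |
| 312 | 5 | 77.7% | 50.8% | 3.69% |
| 314 | 5 | 77.3% | 50.2% | 3.54% |

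The limit stays at 5 from n = 298 to n = 335. The shortfall from 80% is 80 − 78.6 = 1.4 points at 308 and 80 − 77.7 = 2.3 points at 312. Letting the denominator vary binomially changes little: average power is 78.5% for 311 ablated and 77.9% for 314.

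**Step 4: the lower edge.** At n = 297, U(5, 297) = 3.507%, so a fifth stroke fails. At n = 298 it is 3.495% and passes. One subject moves power by 80.6 − 65.6 = 15.0 points. If only 300 subjects are ablated, 300 × 0.9914 = 297.4 are expected to have 30 days of follow-up.

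**The case against.** The strongest reply is that the quoted sentence is true: it is conditional on 300 and reproduces. That stands. There is no arithmetic error in 12.2.6, and the 55% is likewise right for 300. The point concerns only which size the power is stated for.

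Two stronger readings are tempting, and the documents support neither.

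- A reader might infer serious underpowering, because power is below 80% at every size from 301 to 335 and reaches 72.8% at 335. The arithmetic is right, but nothing in the plan points to 320 or 335. Protocol 12.2.6 calls the 26% loss conservative, treats 420 as a ceiling it does not expect to reach, and stops enrolment once 300 evaluable subjects are assured.
- A reader might infer that the trial will be analysed at about 297 with 66% power. That conflicts with the minimum of 300 in Protocol 2.2, 6.1 and 12.2.6. It could arise only if 300 is counted as ablated subjects including exits before day 30, which Protocol 1.11 and SAP 3.1.4.1 leave open.

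It is also fair to say that the loss is small beside the uncertainty in the assumed rate. At 308, a true rate of 1.27% instead of 1.3% restores 80%. The extra subjects also left before any reablation and so carry index-procedure risk only; as an illustration, giving 11 of them a rate of 1.0% yields about 79.1% at 308. Subjects excluded for a non-investigational left-atrial catheter would lower the count slightly. All this limits the importance of the point, but does not make the stated figure right for the denominator the plan defines.

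**Conclusion.** The concern holds in a modest form. Meeting the plan's own target of 300 window completers puts about 312 subjects in the primary analysis, and the enrolment ceiling puts about 308 there. Power at a true rate of 1.3% is then 77.7% to 78.6%, and at 1.8% it is 50.8% to 52.1%. The final size is an inference: it rests on the plan's attrition and reablation inputs and on a constant exit hazard, and the documents do not fix it. The drop to 65.6% below 298 is a risk created by inconsistent counting rules, not a forecast. The pass rule and its error control are unaffected: type I error is below 5% at every size checked from 280 to 420.

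**What to change.** 1. In Protocol 12.2.6 and SAP 3.2.4, state power as about 78 to 79% at the expected 308 to 312 analysed subjects (true rate 1.3%), and about 51 to 52% at 1.8%. The 80% can stay if it is labelled as the value at exactly 300.
2. Add a short table of permitted strokes and power for analysed sizes of about 297 to 315.
3. In Protocol 1.11 and SAP 3.1.4.1, require at least 300 subjects in the primary analysis denominator, so that exits before day 30 without an endpoint stroke do not count toward it. This keeps the analysis above the drop at 298. The window-completion requirement in 12.2.6 can remain beside it.

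The cost is wording in four sections and a slightly less favourable stated power. Within the planned enrolment ceiling no additional subjects are needed, and no visit or success criterion changes.
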